7.7.3 Health-related Quality of Life

For subjects in the melanoma, SCCHN, and TNBC cohorts only, symptom severity will be assessed using the PGIS and select items from the EORTC QLQ-C30 as indicated in the Schedule of Assessments (Table 2).

PGIS: The PGIS is an in-house questionnaire to assess how the subject rates their overall symptom severity (How would you rate the overall severity of your symptoms over the past 7 days – none, mild, moderate, severe, very severe).

EORTC QLQ-C30: The EORTC QLQ-C30 is a 30-item patient-reported outcome questionnaire created to measure broad functioning, symptoms, and health-related quality of life issues across all types of cancers (Aronson 1991). A subset of the EORTC QLQ-C30 items have been selected for administration to reduce patient burden while allowing for key tumor-related and metastasis-related symptoms to be assessed. For melanoma and SCCHN, the selected EORTC QLQ-C30 items measure fatigue (3 items), pain (2 items), and loss of appetite (1 item). For TNBC, the selected EORTC QLQ-C30 items measure fatigue (3 items), pain (2 items), dyspnea (1 item), and loss of appetite (1 item). Each of these items is rated on a 4-point response scale (1 = not at all; 4 = very much).

For subjects in the HCC 1200 mg ascending-dose cohort, symptom severity will be assessed using a generic question to assess severity of symptoms (PGIS) and a cancer-specific instrument for the assessment of hepatobiliary symptoms (FHSI-8) as indicated in the Schedules of Assessments (Table 2).

FHSI-8: The FHSI-8 is a patient-reported outcome questionnaire designed to assess symptoms in patients with pancreatic and hepatobiliary cancers (Yount 2002). It is an 8-item index pain (3 items), fatigue (2 items), weight loss, nausea, and jaundice, with each item scored on a 5-point scale (0 = not at all; 4 = very much).

For subjects in the HCC expansion cohort, symptom severity will be assessed using the PGIS and a modified version of a cancer-specific instrument for the assessment of hepatobiliary symptoms (EORTC QLQ-HCC18-M) as indicated in the Schedules of Assessments (Table 2).

EORTC QLQ-HCC18-M: The EORTC QLQ-HCC18-M is a modified version of the EORTC's HCC-specific module (Blazeby 2004). It consists of 17 patient-reported items intended provide comprehensive HCC-related symptom coverage while minimizing patient assessment burden. The EORTC QLQ-HCC18-M includes 7 items from the EORTC QLQ-C30 measuring dyspnea (1 item), fatigue (3 items), loss of appetite (1 item), and nausea and vomiting (2 items). The EORTC QLQ-HCC18-M includes an additional 10 items from the EORTC's HCC-specific module measuring sense of taste (1 item), wasting (1 item), abdominal bloating (1 item), jaundice (1 item), pruritus (1 item), shoulder pain (1 item), abdominal pain (1 item), fever (2 items), and early satiety (1 item). Each of these items is rated on a 4-point response scale (1 = not at all; 4 = very much).

For subjects in the esophageal adenocarcinoma cohort only, symptom severity will be assessed using the PGIS, select items from the EORTC QLQ-C30, and select items from the EORTC QLQ-OES18 as indicated in the Schedule of Assessments (Table 2). For the esophageal adenocarcinoma cohort, the selected EORTC QLQ-C30 items measure fatigue (3 items) and pain (2 items).

EORTC QLQ-OES18: The EORTC QLQ-OES18 is an 18-item patient-reported outcome questionnaire created to measure functioning, symptoms, and health-related quality of life issues specific to esophageal cancer (Blazeby 2003). A subset of the EORTC QLQ-OES18 items have been selected for administration in the esophageal adenocarcinoma cohort to reduce patient burden while allowing for key tumor-related symptoms to be assessed. The selected EORTC QLQ-OES18 items measure dysphagia (3 items) and reflux pain (2 items). Each of these items is rated on a 4-point response scale (1 = not at all; 4 = very much).

For subjects in the glioblastoma cohort only, symptom severity will be assessed using the PGIS and select items from the EORTC QLQ-BN20 as indicated in the Schedule of Assessments (Table 2).

EORTC QLQ-BN20: The EORTC QLQ-BN20 is a 20-item patient-reported outcome questionnaire created to measure functioning, symptoms, and health-related quality of life issues specific to brain cancer (Taphoorn 2010). A subset of the EORTC QLQ-BN20 items have been selected for administration in the glioblastoma cohort to reduce patient burden while allowing for key functional impacts of the primary tumor to be assessed. The selected EORTC QLQ-BN20 items measure motor dysfunction (3 items), communication deficit (3 items), and drowsiness (1 item). Each of these items is rated on a 4-point response scale (1 = not at all; 4 = very much).

For subjects in the ovarian cancer cohort only, symptom severity will be assessed using the PGIS, select items from the EORTC QLQ-C30, and select items from the EORTC QLQ-OV28 as indicated in the Schedule of Assessments (Table 2). For the ovarian cancer cohort, the selected EORTC QLQ-C30 items measure fatigue (3 items), pain (2 items), and dyspnea (1 item).

EORTC QLQ-OV28: The EORTC QLQ-OV28 is a 28-item patient-reported outcome questionnaire created to measure functioning, symptoms, and health-related quality of life issues specific to ovarian cancer (Greimel 2003). A subset of the EORTC QLQ-OV28 items have been selected for administration in the ovarian cancer cohort to reduce patient burden while allowing for key metastasis-related symptoms to be assessed. The selected EORTC QLQ-OV28 items measure abdominal / gastrointestinal symptoms (6 items). Each of these items is rated on a 4-point response scale (1 = not at all; 4 = very much).

For subjects in the cervical cancer cohort only, symptom severity will be assessed using the PGIS, select items from the EORTC QLQ-C30, and select items from the EORTC QLQ-CX24 as indicated in the Schedule of Assessments (Table 2). For the cervical cancer cohort, the selected EORTC QLQ-C30 items measure fatigue (3 items), pain (2 items), dyspnea (1 item), and loss of appetite (1 item).

EORTC QLQ-CX24: The EORTC QLQ-CX24 is a 24-item patient-reported outcome questionnaire created to measure functioning, symptoms, and health-related quality of life issues specific to cervical cancer (Greimel 2006). A subset of the EORTC QLQ-CX24 items have been selected for administration in the cervical cancer cohort to reduce patient burden while allowing for key metastasis-related symptoms to be assessed. The selected EORTC QLQ-CX24 items measure lymphedema (1 item) and lower back pain (1 item). Each of these items is rated on a 4-point response scale (1 = not at all; 4 = very much).

For subjects in the NSCLC second-line and anti-PD-1/PD-L1 failure cohorts only, symptom severity will be assessed using the PGIS and the NSCLC-SAQ as indicated in the Schedule of Assessments (Table 2).

NSCLC-SAQ: The NSCLC-SAQ and a 7-item patient-reported outcome questionnaire created to measure the cardinal symptoms of NSCLC (McCarrier 2016). Items measure cough (1 item), pain (2 items), dyspnea (1 item), fatigue (2 items), and appetite (1 loss). Each of these items is rated in terms of symptom severity or frequency on a 5-point response scale (1 = none or never; 5 = very severe or always).

8 Statistics

CCI

[REDACTED]

[REDACTED]

8.1.1 Dose Escalation

The sample size for the dose-escalation part of the trial is not based on any statistical assumptions; rather, it follows the “3 + 3 rule,” a well-established methodology in the design of dose-finding trials in oncology.

This trial plans for up to 6 cohorts (1, 3, 10, 20, and 30 mg/kg, and 2400 mg flat dose) of 3 subjects to be treated at each escalating dose level and with typical DLT driven expansions to 6 subjects and at the MTD. After the appearance of a single DLT, the cohort for that dose level will be expanded to 6 subjects. Therefore, the number of subjects enrolled in the dose-escalation phase of the trial will depend on the number of dose escalation steps needed to reach the MTD.

After the 1 and 3 mg/kg cohorts have completed the DLT evaluation period, a PK / CCI analysis will be performed. Depending on the results of this analysis for PBMC PD-L1 receptor occupancy, a decision will be made to initiate up to 2 cohorts of 3 subjects each, one at 0.1 mg/kg and one at 0.3 mg/kg, which will increase on the second dose and all subsequent doses to a 1200 mg/infusion flat dose. No DLT evaluations will be performed in this flexible cohort.

After the MTD has been reached or the 20 mg/kg cohort has been declared by the SMC as the highest non-MTD dose assessed, then further PK/CCI analyses will be performed. If deemed necessary, the 1, 3, 10, and 20 mg/kg cohorts may each enroll up to an additional 10 subjects (up to 40 total) for the purpose of PK / CCI modeling. On the second dose and all subsequent doses, the 1 mg/kg cohort may increase to a 1200 mg/infusion flat dose. No DLT evaluations will be performed in these supplemental cohorts.

With the safety of the 30 mg/kg cohort established, a fixed dose cohort of 2400 mg once every 2 weeks will be enrolled in a 3 + 3 design with SMC evaluation after the first 3 subjects.

Accordingly, the expected total sample size in the dose-escalation part of the trial will be between 3 and 82 subjects.

8.1.2 Expansion Cohorts

CCI

[Redacted content]

Table 12 **The 95% Exact (Clopper-Pearson) Confidence Intervals for ORR Based on 30 Enrolled Subjects**

ORR	95% Exact Confidence Interval
0.20	(0.077, 0.386)
0.30	(0.147, 0.494)
0.40	(0.227, 0.594)
0.50	(0.313, 0.687)
0.60	(0.406, 0.773)
0.70	(0.506, 0.853)

HCC ascending-dose cohort

In order to further assess the tolerability and safety of MSB0011359C in subjects with HCC, up to 36 subjects may be enrolled in the ascending dose part of the HCC cohort. Six subjects will be enrolled at 3 mg/kg once the 3 mg/kg dose level in the dose escalation part of the trial has been cleared by the SMC. Thirty subjects will be enrolled at a 1200 mg flat dose once the 20 mg/kg dose level in the dose escalation part of the trial has been cleared by the SMC.

HCC second-line or sorafenib-intolerant cohort

Up to 70 subjects will be enrolled in the HCC second-line or sorafenib-intolerant cohort at the dose selected by the SMC during the dose-escalation part of the trial, for the purpose of assessing efficacy based on the BOR. An initial enrollment of 30 subjects will accrue if > 6 of 30 subjects in the HCC 1200 mg flat-dose ascending-dose cohort have a response (that is an ORR of at least 20%). The primary analysis will be 24 weeks after the 60th subject started treatment. The analysis will include the 30 subjects from the HCC 1200 mg flat-dose ascending-dose cohort and 30 subjects from the HCC second-line or sorafenib-intolerant cohort (assumes a similar target population as per the inclusion criteria). An additional 40 subjects may subsequently be enrolled in order to gather additional safety data.

With 60 subjects treated (30 subjects from the HCC 1200 mg flat-dose ascending-dose cohort and 30 subjects from the HCC second-line or sorafenib-intolerant cohort), the study has approximately 88% power to rule out a $\leq 20\%$ ORR (null hypothesis) when the true ORR is 35% at the 10% type I error rate (1-sided).

NSCLC anti-PD-1 / anti-PD-L1 failure cohort

With 80 subjects treated, the study has approximately 92% and 99% power to rule out a $\leq 5\%$ ORR (null hypothesis) when the true ORR is 15% and 20%, respectively, at the 5% type I error rate (1-sided).

Melanoma anti-PD-1 / anti-PD-L1 failure cohort

The goal of this cohort is an exploration of anti-PD-L1 retreatment and initial clinical responses as a way to show confidence in the proof-of-mechanism of the addition of TGF β inhibition to the anti-PD-L1 mechanism. With 30 subjects who were treated with prior anti-PD-1 / anti-PD-L1 therapy, the study has 87% power to rule out a 5% ORR when the true ORR is 20% with 1-sided 0.1 alpha.

NSCLC second-line cohort

With 30 second-line subjects treated at 1200 mg/infusion, the study has approximately 82% power to rule out a $\leq 20\%$ ORR (null hypothesis) when the true ORR is 40% at the 10% type I error rate (1-sided).

An interim analysis will occur when the 30 subjects are evaluable for response assessment at 12 weeks (that is, have either completed the second tumor reassessment at Week 12 or discontinued the study before Week 12). If ≤ 4 responders are observed at the interim analysis, no further subjects will be enrolled into the NSCLC second-line cohort.

Pancreatic adenocarcinoma, CRC, and cervical cancer cohorts

With 30 subjects treated, the study has approximately 79% power to rule out a $\leq 10\%$ ORR (null hypothesis) when the true ORR is 25% at the 10% type I error rate (1-sided).

Ovarian cancer, TNBC, and esophageal adenocarcinoma cohorts

With 30 subjects treated, the study has approximately 87% power to rule out a $\leq 15\%$ ORR (null hypothesis) when the true ORR is 35% at the 10% type I error rate (1-sided).

Glioblastoma cohort

With 30 subjects treated, the study has approximately 97% power to rule out a $\leq 50\%$ DCR (null hypothesis) when the true DCR is 80% at the 5% type I error rate (1-sided).

SCCHN cohort

With 30 subjects treated, the study has approximately 87% power to rule out a $\leq 15\%$ ORR (null hypothesis) when the true ORR is 35% at the 10% type I error rate (1-sided).

All expansion cohorts

Except for the glioblastoma cohort, the primary efficacy endpoint for the dose expansion-part of the trial is the confirmed BOR according to RECIST 1.1 as adjudicated by the Independent Endpoint Review Committee (IRC) and will be evaluated by confirmed ORR. For glioblastoma, the primary endpoint will be disease control.

For each cohort separately (except for the HCC cohort), upon continuation of the cohort up to the targeted sample size, the primary analysis will occur 24 weeks after the start of treatment in the

last subject enrolled. For the HCC cohort, the primary analysis will be after 60 subjects (including 30 subjects from the ascending dose and 30 subjects from the second line expansion cohort).

The total sample size for the expansion cohorts is expected to be up to approximately 566 subjects.

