Subjects from either the dose-escalation or the expansion portions of the trial who have experienced stable disease (SD), a partial response (PR), or a complete response (CR) should be treated through the end of 12 months, although additional treatment is possible. If the Investigator believes that a subject may benefit from treatment beyond 12 months, it may be permissible after discussion with the Medical Monitor and the Sponsor Medical Responsible. In the case of PD, subjects should continue treatment through their next tumor assessment, if they meet the criteria described in this protocol. If there is further evidence of PD thereafter, trial treatment should be discontinued; however continued treatment is possible in consultation with the Medical Monitor. For subjects who achieve SD, a CR or PR on MSB0011359C therapy and then subsequently develop disease progression after stopping therapy, but prior to the end of the trial, 1 re-initiation course of treatment at the same dose and schedule and treatment duration up to 12 months is allowed at the discretion of the Investigator and agreement of the trial Medical Responsible. The Investigator will need to confirm that the benefit of re-initiating treatment outweighs any risk involved, such as that which led to initial treatment discontinuation. Moreover, for subjects in which BOR was SD, the Investigator should confirm no other reasonable treatment options are available.

Subjects will be monitored and assessed for safety and efficacy parameters at regular intervals throughout the trial.

Planned number of subjects:

[figure not shown]
Dose escalation: from 3 to 82 subjects.

Expansion: Up to approximately 566 subjects.

[figure not shown]
Primary endpoints:

The primary endpoints for the dose-escalation part of the trial are the:

- Number, severity, and duration of TEAEs according to the NCI Common Terminology Criteria for Adverse Events (CTCAE) v4.03

CCI

CCI

CCI

CCI

Diagnosis and key inclusion and exclusion criteria:

Key inclusion criteria for the dose escalation include:

1. Ability to understand the purpose of the study, provide signed and dated informed consent, and able to comply with all procedures
2. Male or female subjects aged ≥ 18 years
3. Histologically or cytologically proven metastatic or locally advanced solid tumors, for which no effective standard therapy exists or standard therapy has failed
4. Life expectancy ≥ 12 weeks as judged by the Investigator

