The sample size for the dose-escalation part of the trial is not based on any statistical assumptions; rather, it follows the “3 + 3 rule”, a well-established methodology in the design of dose-finding trials in oncology.

This trial plans for 6 cohorts (1, 3, 10, 20, and 30 mg/kg, and 2400 mg flat dose) of 3 subjects to be treated at each escalating dose level and with typical DLT driven expansions to 6 subjects and at the MTD. Additional cohorts at low-dose levels for PK profile and PK / PharmDyn modeling may be enrolled as well as HCC. Accordingly, the expected total sample size in the dose-escalation part of the trial will be between 3 and 82 subjects.

Except for the glioblastoma cohort, the primary efficacy endpoint for the dose-expansion part of the trial is the confirmed BOR according to RECIST 1.1 as adjudicated by the IRC. For glioblastoma, the primary endpoint will be disease control according to RANO as adjudicated by the IRC.

CCI

HCC, ascending-dose cohort: Up to 36 subjects will be enrolled for the purpose of tolerability and safety assessment.

There will be one planned interim analysis for internal planning purposes. There is no multiplicity adjustment applied to the interim analysis. The interim analysis will occur when the first 30 subjects treated at the MTD or dose level selected for investigation in the expansion cohorts are evaluable for response assessment at 12 weeks (that is, have either completed the first tumor reassessment at Week 12 or discontinued the study before Week 12).

HCC, second-line or sorafenib-intolerant cohort: Up to 70 subjects will be enrolled in the HCC expansion cohort at the dose selected by the SMC during the dose-escalation part of the trial, for the purpose of assessing additional safety data and efficacy based on the BOR. An initial enrollment of 30 subjects will occur if > 6 of 30 subjects in the HCC 1200 mg flat-dose ascending-dose cohort have a response (that is an ORR of at least 20%). The primary analysis for this cohort will include the 30 subjects from the HCC 1200 mg flat-dose ascending-dose cohort and 30 subjects from the HCC second-line or sorafenib-intolerant cohort (assumes a similar target population as per the inclusion criteria). An additional 40 subjects may subsequently be enrolled in order to gather additional safety data.

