With 30 subjects treated, the study has approximately 87% power to rule out a $\leq 15\%$ ORR (null hypothesis) when the true ORR is 35% at the 10% type I error rate (1-sided).

The total sample size for the study (dose escalation and dose expansion) is expected to be up to approximately 642 subjects.

Statistics for continuous variables may include means, medians, ranges, and appropriate measures of variability. Qualitative variables will be summarized by counts and percentages. The uncertainty of estimates will be assessed by confidence intervals. The results of the safety evaluations will be tabulated and displayed by dose level / expansion cohort. Only exploratory statistical analysis will be performed. Descriptive statistics will be examined for indications of dose-related toxicity.

Listings will be produced upon completion of each dose-escalation cohort of subjects and the decision as to whether to proceed with dose-escalation, dose-reduction or to enroll another cohort at the same dose level will be determined by reviewing these data. Full details of the planned analyses will be described in the trial Statistical Analysis Plan, separately for the dose-escalation part and the expansion part.

Schedule of Assessments

Table 1 Schedule of Assessments – Dose Escalation Phase

Measure	Screening Assessments	Treatment Phase (-3 / +1 days) ^a											EoT Visit	Safety Follow-up		Long-term Follow-up ^{b,c}	
	Day -28 to First Treatment	V1	V2	V3	V4	V5	V6	V7	V7	V8	V9	V10	Until Progression	On the Day of or Within 7 Days of Decision to Discontinue ^d	28 Days (± 5 days) after Last Treatment ^e	10 Weeks (± 2 weeks) after Last Treatment	Every 12 Weeks (± 2 weeks)
		W1	W1	W2	W3	W4	W5	W7	W7	W9	W11	W13					
Written informed consent	X																
Inclusion / exclusion criteria	X	X															
Medical history	X																
Cancer disease history	X																
Prior anticancer drug / radiotherapy / procedures	X																
Other prior medications	X																
Demographic data	X																
HBV and HCV testing	X																
Ophthalmology examination including slit lamp evaluation inclusive of the anterior segment and with visual acuity ^f	X																
Physical examination ^f	X	X	X	X	X	X	X	X		X	X	X	6-weekly	X	X	X	
Dermatological assessment ^g	X				X		X	X		X	X	X	6-weekly	X	X	X	
12 lead ECG ^h	X	X/X ^h	X	X	X/X ^h		X/X ^h	X				X	6-weekly normal ECGs	X	X		

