8.6 Interim and Additional Planned Analyses

Enrollment of expansion cohorts will not be stopped for the purpose of conducting their respective interim analyses but will stop if futility is met as specified.

Dose Escalation Part

In the dose-escalation part, the trial data will be evaluated before decision is made to go to the next dose level or to start with treatment in the expansion part.

Expansion Part

For all expansion cohorts except glioblastoma cohort, the endpoints in these interim analyses are ORR (confirmation is not required). For glioblastoma, the endpoint in the interim analysis will be DCR. There is no multiplicity adjustment is applied to the interim analyses. The decision rules at the interim analyses serve as guidance and are non-binding. In the absence of a control arm, outcomes in this single arm study have to be interpreted with caution, both at interim and final analyses.

CCI

HCC ascending-dose cohort

An interim analysis will be conducted 12 weeks after the final subject in the ascending-dose portion received their first dose.

If ≤ 6 responses are observed in the 30 subjects at the interim analysis, the enrollment into HCC second-line or sorafenib-intolerant cohort will be stopped. This decision criterion has 39% probability of rejecting the null hypothesis if the true response rate is 20% and 6% probability of rejecting the alternative hypothesis if the true response rate is 35%.

Enrollment of HCC second-line or sorafenib-intolerant cohort will not be stopped for the purpose of conducting this interim analysis but will stop if futility is met as specified.

HCC second-line or sorafenib-intolerant cohort

No interim analysis is planned.

NSCLC anti-PD-1 / anti-PD-L1 failure cohort

One interim analysis is planned for this cohort 12 weeks after the 40th subject in this cohort started treatment.

- If ≤ 2 responses are observed in the 40 subjects at the interim analysis, the enrollment will be stopped. This decision criterion has 32% probability of rejecting null hypothesis if the true response rate is 5% and 5% probability of rejecting alternative hypothesis if the true response rate is 15%.
- If 3 to 4 responses are observed at the interim analysis, the enrollment will be temporarily stopped until the first 40 subjects have completed tumor assessment at Week 24. After a review of the totality of data, including duration of response, DCR, and safety, the Sponsor will make a decision as to whether to resume the accrual.

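### The HCC gate of more than 6 of 30 is misdescribed as an ORR of at least 20%, and the Synopsis total of 642 does not equal its own parts, 82 + 566 = 648

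*Protocol*

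**What the plan says.** **HCC gate.** Section 8.1.2 of the Protocol (HCC second-line or sorafenib-intolerant cohort) makes the initial 30 subjects conditional on more than "6 of 30 subjects in the HCC 1200 mg flat-dose ascending-dose cohort have a response (that is an ORR of at least 20" per cent). The Synopsis, under Statistical methods, repeats both the count and the explanation: "flat-dose ascending-dose cohort have a response (that is an ORR of at least 20%). The primary analysis for this cohort will include the 30". Section 8.6 gives the complementary rule for the HCC ascending-dose cohort: if 6 or fewer "responses are observed in the 30 subjects at the interim analysis, the enrollment into HCC second-line or sorafenib-intolerant cohort will be stopped". It attaches operating characteristics to that rule: "39% probability of rejecting the null hypothesis if the true response rate is 20% and 6% probability" of rejecting the alternative at a true rate of 35%. Section 8.6 also says that its decision rules are non-binding guidance.

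**Timing of the gate.** The Synopsis and 8.1.2 word the condition as though the initial 30 second-line subjects wait for it. Section 8.6 says that their enrollment is not paused for the interim analysis but stops if futility is met.

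**Study total.** Under Planned number of subjects the Synopsis gives "Dose escalation: from 3 to 82 subjects" and "Expansion: Up to approximately 566 subjects". Section 5.1.5 gives the same two figures. Later the Synopsis states: "The total sample size for the study (dose escalation and dose expansion) is expected to be up to approximately 642 subjects".

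**The concern.** A decision threshold should have one meaning. At exactly 6 responses in 30, someone working from the percentage in the Synopsis or 8.1.2 could argue that the gate is met, while 8.6 says stop. This is also the worst place for ambiguity: 20% is the null ORR for the cohort, so the percentage as worded would pass a result sitting exactly on the null.

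The total is a simpler matter. It is defined as escalation plus expansion, and both parts are printed in the same synopsis. If it is not their sum, one of the three numbers is wrong, and maximum enrollment is a figure that ethics committees and authorities read from the Synopsis.

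**Working it through.** **1. Inputs for the gate.** n = 30; continue if more than 6 respond (Synopsis, 8.1.2); stop at 6 or fewer (8.6); true ORR 20% (null) and 35% (alternative); stated results 39% and 6% (8.6). X is the number of responders, binomial(30, p).

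**2. Reproduce the plan's figures, and test the rival reading.**

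| Rule | P(continue), p = 0.20 | P(stop), p = 0.35 |
|---|---|---|
| Continue at X ≥ 7 (the count) | P(X ≥ 7) = 0.3930 | P(X ≤ 6) = 0.0586 |
| Continue at X ≥ 6 (the percentage) | P(X ≥ 6) = 0.5725 | P(X ≤ 5) = 0.0233 |
| Stated in 8.6 | 39% | 6% |

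Only the first row reproduces the plan.

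**3. Translate the count into a rate.** 6/30 = 20.0%, a stop. 7/30 = 23.3%, the lowest result that continues.

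**4. How often the wordings disagree.** They differ only at X = 6. That probability is 0.5725 − 0.3930 = 0.1795 at a true ORR of 20%, and 0.0586 − 0.0233 = 0.0353 at 35%.

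**5. Cross-check on how 8.6 counts.** For the NSCLC anti-PD-1 / anti-PD-L1 failure cohort, 8.6 stops at 2 or fewer of 40 and states: "This decision criterion has 32% probability of rejecting null hypothesis if the true response rate is 5% and 5% probability of rejecting alternative hypothesis" at a true rate of 15%. Exact binomial, n = 40: P(X ≥ 3) = 0.3233 at p = 0.05 and P(X ≤ 2) = 0.0486 at p = 0.15. Both agree. A stop at 1 or fewer would give 0.6009 and 0.0121. So 8.6 treats the stated number as a stop in both cohorts.

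**6. Power at 60 HCC subjects.** The smallest success count that holds a one-sided 10% level is 17 (16 gives 0.131; 17 gives 0.077). Power at 35% is then 0.890, in line with the stated approximate 88%. Treating the gate as binding gives 0.866 with 7 or more and 0.883 with 6 or more. All three are close to 88%, so this figure cannot decide between the readings. The pair in 8.6 is stated for the gate itself and can.

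**7. Rebuild the two parts of the total.**

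- Escalation (8.1.1): 6 cohorts × 6 + 2 low-dose cohorts × 3 + 40 additional PK subjects = 36 + 6 + 40 = 82.
- Expansion (5.3.1.2, Synopsis, 8.1.2): NSCLC biomarker 15 + 15 = 30; HCC ascending dose 36; HCC second line 70; NSCLC failure 80; melanoma 30; NSCLC second line 80; and eight cohorts of 30 (pancreatic, CRC, cervical, ovarian, TNBC, esophageal, glioblastoma, SCCHN) = 240. Sum: 30 + 36 + 70 + 80 + 30 + 80 + 240 = 566.
- Total: 82 + 566 = 648. Gap: 648 − 642 = 6, and 6/648 = 0.9%.

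Both parts rebuild exactly, so 642 is the figure that is off. It equals 76 + 566, as if one six-subject escalation cohort had been left out. That origin is an inference; the documents do not state it.

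**The case against.** The strongest reply is that no rule conflicts. More than 6 in the Synopsis and 8.1.2 is the exact complement of 6 or fewer in 8.6, so every possible result has one outcome. An explicit count governs its own explanation, and more than 6 of 30 does imply an ORR of at least 20%; the explanation is loose only because it presents an implication as an equivalence. The rules are non-binding anyway. This stands as a limit on impact: the intended rule is not in doubt once 8.6 is read. It does not make the stated threshold correct.

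On the total, both 642 and 566 are described as approximate, Section 5.1.5 allows the final size to vary, and the boundary for HCC is not uniform. The Synopsis mentions HCC just before giving the 82, and SAP Section 6 groups the HCC 3 mg/kg cohort with dose escalation. Had those six subjects been counted in both parts, 642 would be right. They were not: 82 is fully accounted for by 36 + 6 + 40 without any HCC subjects. Moving them from one part to the other would not change the sum. Rounding does not explain the gap either, since the parts rebuild exactly.

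It is also fair that the enrollment wording is secondary, because 8.6 already covers it. Nor is a live decision shown to depend on any of this: the Protocol version is dated 22 June 2021, and SAP Section 6.1 reports a CSR approved on 02 March 2021. Both points support a low rating.

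**Conclusion.** Both errors hold, and both are minor. The percentage attached to the HCC gate is wrong: the operative rule is at least 7 of 30, an observed ORR of at least 23.3%. The misstatement bears on one result, 6/30, which has probability 17.9% at a true ORR of 20% and 3.5% at 35%. The study total is 6 short of the sum of its stated parts.

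The gate conclusion rests on exact binomial calculation and on reading the 39% as the chance of continuing under the null, the only reading that fits the rule. The total rests on the maxima printed in the Protocol. The design, the cohort sizes, the stopping rules and the stated powers are unaffected.

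**What to change.** - In the Synopsis (Statistical methods, HCC second-line cohort) and in Section 8.1.2, replace the parenthetical percentage with: at least 7 of 30, observed ORR at least 23.3%.
- In the Synopsis, change the study total from about 642 to about 648.
- In the same two HCC paragraphs, reword the condition on the initial 30 subjects to match 8.6: enrollment continues during the interim analysis and stops if futility is met.

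Section 8.6 and the stated powers stay as they are. The cost is two parentheticals, two verbs and one number, with no change to the design or analysis.
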